12 hours for children >2 months old.^{12, 23} The dose is adjusted to a target anti-Xa activity of 0.2-0.5 IU/mL.^{23, 46, 47} In the absence of prior trials in children, the same target anti-Xa activity recommended in adults will be used in this trial.²³ Among post-operative orthopedic patients on prophylactic dose of LMWH, the mean peak anti-Xa activity on Days 1, 3, 4 and 10 were 0.29, 0.25, 0.33 and 0.37 IU/mL. In acutely ill medical patients, the prophylactic dose of LMWH achieved anti-Xa activity of 0.21 to 0.41 IU/mL. Dose calculations are completed per local standards. An example dose calculation work sheet is provided in Appendix 2.

Rationale for Dose Selection/Regimen

The selection of doses to be used in this trial is based on commonly used doses for the drug.¹⁷ When prescribing enoxaparin in children as prophylaxis against DVT, the starting dose is typically 0.75 mg/kg for children ≤2 months old or 0.5 mg/kg (maximum of 30 mg) for older children. The present trial will utilize this dose as a starting point because of the proven tolerability in clinical care. The maximum dose is based on FDA-approved doses in adults. At these doses, enoxaparin has been shown to be safe without any significant increase in the risk of clinically relevant bleeding.⁴³

Reconstitution

Dilute Enoxaparin Sodium Injection, USP with sterile water for injection or normal saline. Draw up the appropriate dose in a polypropylene plastic tuberculin syringe sealed with a rubber tip cap.

Storage and Stability Requirements

Enoxaparin should not be stored above 25°C and should not be frozen.⁴⁵ When stored at 20°C to 22°C, enoxaparin, 1.2 mg/ml in normal saline, was stable for up to 48 hours. Enoxaparin when repackaged from commercial 0.3 mg syringes of enoxaparin, 100 mg/mL, into tuberculin syringes retained activity and sterility and remained pyrogen free for up to 10 days at 3°C. Undiluted enoxaparin lost activity within 2 days at 22°C. Enoxaparin diluted with sterile water for injection to 20 mg/ml, and stored at room temperature or under refrigeration, was stable for up to 4 weeks in glass or prefilled syringes, as measured by anti-Xa activity.

Handling

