Subjects randomized to the treatment arm will receive enoxaparin adjusted to the target anti-Xa activity. Subjects randomized to the control arm will not receive placebo because of ethical concerns of inducing pain with subcutaneous administration without any potential for direct benefit. All subjects in the study will undergo the remaining study procedures.

TREATMENT REGIMEN WITH ENOXAPARIN

The 1st dose of enoxaparin be given <24 hours after insertion of the CVC. The initial dose will be 0.75 mg/kg for children ≤2 months old or 0.5 mg/kg (maximum of 30 mg) for older children (Table 1). The initial dose will be doubled in obese children (refer to Appendix I and II) and halved in children with renal insufficiency (estimated creatinine clearance calculated by the Schwartz equation $<75 \text{ mL/min/1.73 m}^2$).⁴⁹ The clinical nurse will give enoxaparin subcutaneously every 12±2 hours after the first dose until removal of the CVC, or earlier upon discharge from the ICU, radiologic diagnosis of CADVT, start of therapeutic anticoagulation, clinically relevant bleeding develops, HIT is diagnosed, or 28 days after insertion of the CVC.

Administration

Route. Enoxaparin is to be administered by subcutaneous route per local site clinical procedures.

Site. In children <10 kg or <1 year of age, the thigh is the preferred site of administration. Alternate between the left and right thigh. In children ≥10 kg or ≥1 year of age, the abdomen is the preferred site. For children who do not have sufficient subcutaneous tissue in the abdomen, the anterolateral thigh may be used as secondary site for administration.

Table 1: Initial dose

Age	Drug	Dose/ Potency*	Dose Frequency	Route	Regimen/ Treatment Period†	Use
Children ≤2 mos.	Enoxaparin	0.75 mg/kg	Q12 hours	Subcutaneous	Until CVC is removed	Experimental
Children >2 mos.	Enoxaparin	0.5 mg/kg (maximum of 30 mg)	Q12 hours	Subcutaneous	Until CVC is removed	Experimental

*The initial dose will be doubled in obese children (refer to Appendix I and II) and halved in children with renal insufficiency (estimated creatinine clearance calculated by the Schwartz equation $<75 \text{ mL/min/1.73 m}^2$).⁴⁹ †Enoxaparin treatment will stop before the CVC is removed upon discharge from the ICU, radiologic diagnosis of CADVT, start of therapeutic anticoagulation, clinically relevant bleed develops, HIT is diagnosed, or 28 days after insertion of the CVC, whichever comes first.

Titration dose

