The dose of enoxaparin will be adjusted to a target anti-Xa activity of 0.2-0.5 IU/mL.^{23, 46, 47} The target anti-Xa activity is a peak level and, therefore, timing is extremely important. The peak level must be drawn 4-6 hours after the dose is actually administered. If the child has other labs ordered which are not time dependent, the other labs should be drawn at the same time the enoxaparin peak level is needed.

Using standard methods, anti-Xa activity will be measured 4-6 hours after a dose at the following time points:

1. After the first 3 doses. If needed, the dose will be adjusted to achieve the target anti-Xa activity. See Table 2 for dose titration.
2. After the 3rd dose of a dose titration until the target anti-Xa activity is reached. Once the anti-Xa activity is within target, the dose will be maintained. See Table 2 for dose titration.
3. Weekly to ensure adequate dosing. Similar dose titration as listed in Table 2 will be done to achieve adequate dosing.

Table 2: Enoxaparin Dosage Titration

Anti-Xa Activity	Enoxaparin Dose Titration	Next Anti-Xa Activity Check
<0.10 IU/mL	Increase dose by 20%	After 3 rd dose.
0.10-0.19 IU/mL	Increase dose by 10%	After 3 rd dose.
0.20-0.50 IU/mL	Keep same dosage	Weekly
0.51-1.00 IU/mL	Decrease dose by 10%	After 3 rd dose.
>1.00 IU/mL	Hold all doses until anti-Xa is 0.3, IU/mL, then decrease dose by 20%	Before next dose and every 12 hours, until anti-Xa <0.3 IU/mL

(Modified from Monagle P, et al. *Chest*, 2001, 119:344S)⁵⁰

Discontinuing enoxaparin

The child will be removed from the study and Enoxaparin will be discontinued for the purposes of the study if ANY the following occur:

1. A clinically relevant bleeding event
 - a. Drop in Hb of ≥ 2 g/dl in 24 hours
 - b. Blood product transfused for the bleeding event
 - c. Required medical or surgical intervention to restore hemostasis
 - d. In a critical organ (*i.e.*, retroperitoneum, pulmonary, intracranial or central nervous system)
2. HIT is diagnosed (*i.e.*, positive serotonin release assay)

Holding the Dose

Enoxaparin will be stopped temporarily if ANY the following occur

1. Coagulopathy (*i.e.*, international normalized ratio >2.0, activated partial thromboplastin time >50 seconds or platelet count <50,000/mm³) develops

2. 12 hours before surgery or invasive procedure
3. In cases of suspected HIT (*i.e.*, an unexplained decrease in platelet count $<50,000/\text{mm}^3$ or by 50% of baseline value in the ICU).

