APPENDIX II

DOSE CALCULATION WORKSHEET

Subject #:	Subject Name:	Subject MRN:
Age:	Weight (kg):	Height (cm):
Date:	Dose Sequence: (e.g. 1-3, 4-6, etc)	BMI (only applicable for age 2-18)
	kg	cm
		kg/m ²

SECTION I					
Instructions for initial dose (#1-3), otherwise skip to Section II					
1. Using the table below, select dose for patient based on patient's age: _____ mg/kg					
Age	Drug	Dose/Potency	Dose Frequency	Route	Regimen/ Treatment Period
Children ≤2 months	Enoxaparin	0.75 mg/kg	Every 12 hours	Subcutaneous	Until CVC is removed
Children > 2 months	Enoxaparin	0.5 mg/kg (maximum of 30 mg)	Every 12 hours	Subcutaneous	Until CVC is removed
2. Evaluate patient's characteristics for dose modification.					
a. For subject between the ages of 0 to 2 years old, does the weight for the corresponding height exceed the 95th percentiles weight provided in Appendix II? _____ Yes _____ No					
• If yes, double the dose due to obesity					
b. For subject between the age of 2 to 18 years old, does the BMI for the corresponding age exceed the 95th percentiles BMI provided in Appendix III? _____ Yes _____ No					
• BMI = (Weight (in kilograms)/Height (in meters ²))					
_____ kg/m ² = (_____ kg / (_____ m) ²)					
• If yes, dose is doubled due to obesity.					
3. Based on patient's age and obesity status, input dose into Section II under "mg/kg Dose Selected"					

SECTION II		
mg/kg Dose Selected	Serum Creatinine	Anti-Xa Activity
mg/kg	mg/dL	IU/mL
Step 1: Renal function		

 Determine the subject's k constant: 
 k is 0.33 in premature infants through the first year of life k is 0.43 for term infants through the first year of life k is 0.55 in boys age 2-12 years old and girls of any age k is 0.70 in adolescent boys over the age of 12 Calculate Glomerular Filtration Rate using Schwartz Equation: $GFR = k * Height (cm) / SCr (mg/dL)$ 		
_____ mL/min/1.73m ² = (_____ x _____ cm) / (_____ mg/dL)		
Using the Schwartz equation, is GFR less than 75 mL/min/1.73 m ² ? _____ Yes _____ No		
• If yes, halved the dose selected from Section I due to renal insufficiency.		
What is the current dose based on renal function? _____ mg/kg		
Step 2: Dose Calculation (1st Dose)		
Take the dose (mg/kg) determined in step 1 and multiply it by the patient's weight (kg)		
_____ mg (maximum of 30mg) = _____ mg/kg (dose) x _____ kg (weight)		
Step 3: Dose Titration (Subsequent Doses)		

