Select the appropriate titration factor corresponding to the anti-Xa activity.		
Anti-Xa Activity	Enoxaparin Dose Titration	Titration Factor (TF)
<0.1 IU/mL	Increase dose by 20%	1.2
0.1-0.19 IU/mL	Increase dose by 10%	1.1
0.2-0.5 IU/mL	Keep same dosage	1
0.51-1 IU/mL	Decrease dose by 10%	0.9
>1 IU/mL	Hold all doses until anti-Xa is 0.3, IU/mL, then decrease dose by 20%	0.8
Next Anti-Xa Activity Check		
After 3 rd dose		
Check in 1 week		
After 3 rd dose		
Before next dose and every 12 hours, until anti-Xa <0.3 IU/mL		
Subsequent Dose		
_____ mg (maximum of 30mg) = _____ mg (previous dose) x _____ (TF)		
Step 4: Volume Calculation		
Take the dose (mg) calculated in Step 2 or Step 3 and divide it by 20 mg/mL concentration for doses <10mg. Use 100mg/mL concentration for doses ≥10mg to obtain the volume that needs to be dispensed in a Vanish Point or another suitable syringe.		
_____ mL = _____ mg / _____ mg/mL (****Round the dose volume to the nearest hundredth****)		
Step 5: Dispensing		
Dispensed _____ mL (step 4) of enoxaparin in a Vanish Point or other suitable syringe. Dose is stable for 24 hours. Discard any unused drug.		

Pharmacist's or Designee's Signature/Print Name: _____ Date: _____

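### Appendix II caps every titrated enoxaparin dose at 30 mg, while Table 2 titrates upward to the anti-Xa target with no stated maximum; the two pages must be reconciled

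*Combined protocol and SAP*

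**What the plan says.** **Starting dose.** The section Treatment Regimen with Enoxaparin sets "The initial dose will be 0.75 mg/kg for children ≤2 months old or 0.5 mg/kg (maximum of 30 mg) for older children (Table 1". The Trial Summary, Drug Dose and the Rationale for Dose Selection likewise attach the 30 mg maximum to the dose at which treatment starts. The Rationale adds that the maximum derives from approved adult doses, without saying whether it also limits later doses.

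**Titration.** The section Titration dose, with Table 2, raises the dose by 20% when anti-Xa is below 0.10 IU/mL and by 10% when it is 0.10-0.19 IU/mL. Levels are repeated "After the 3rd dose of a dose titration until the target anti-Xa activity is reached". No maximum appears in the text or in Table 2.

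**Worksheet.** Appendix II, Step 2, limits the first dose: "mg (maximum of 30mg) = _____ mg/kg (dose) x _____ kg (weight". Step 3 puts the same limit on all subsequent doses: "mg (maximum of 30mg) = _____ mg (previous dose) x _____ (TF". Its titration factors for increases (1.2 and 1.1) agree with Table 2.

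**Status of the worksheet.** Drug Dose says "Dose calculations are completed per local standards" and calls the worksheet an example.

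**The concern.** For a child at 30 mg whose level is low, the two pages give different doses of study drug, and nothing in the documents says which governs. Because the worksheet is only an example, one site could follow it and another could follow Table 2 without either deviating from the protocol.

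At stake is how the intervention is delivered to heavier children. Treatment is defined as enoxaparin adjusted to an anti-Xa target. Outcome Measures lists time to target anti-Xa as a feasibility outcome. Statistical Considerations models ETP over D1-D4, the relation of ETP to anti-Xa, predictors of reaching target, and joint models with CADVT and bleeding. If the ceiling varies by site, the dose behind those later measurements varies with it. A child held at 30 mg below target also has no defined place in the time-to-target analysis.

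**Working it through.** The plan states no weight threshold for this point, so there is no figure to reproduce.

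**Inputs.** Starting dose is 0.5 mg/kg for children older than 2 months, doubled in obesity and halved in renal insufficiency (Treatment Regimen, Table 1). Upward factors are 1.1 and 1.2 (Table 2, Appendix II). The cap is 30 mg (Appendix II, Step 3).

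**Formulas.** The starting dose equals the cap at weight = 30 / (mg/kg). The first upward step exceeds the cap above weight = 30 / (mg/kg × factor).

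| Starting dose | First +20% step cut above | First +10% step cut above | No increase possible from |
|---|---|---|---|
| 0.5 mg/kg (standard) | 30/(0.5×1.2) = 50.0 kg | 30/(0.5×1.1) = 54.5 kg | 30/0.5 = 60 kg |
| 1.0 mg/kg (obesity) | 30/(1.0×1.2) = 25.0 kg | 30/(1.0×1.1) = 27.3 kg | 30/1.0 = 30 kg |
| 0.25 mg/kg (renal) | 30/(0.25×1.2) = 100 kg | 30/(0.25×1.1) = 109.1 kg | 30/0.25 = 120 kg |

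**Examples at 0.5 mg/kg.**
- 50 kg: start 25 mg; +20% gives 30 mg on both pages.
- 58 kg: start 29 mg; Table 2 gives 31.9 or 34.8 mg; the worksheet gives 30 mg, a rise of only 3.4%.
- 60 kg and over: start 30 mg; Table 2 gives 33 or 36 mg; the worksheet gives 30 mg.

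Just above the thresholds the difference is small: Step 4 of the worksheet rounds to 0.01 mL, which is 1 mg at 100 mg/mL.

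**Repeated steps.** After two +20% steps the cap binds above 30/(0.5×1.44) = 41.7 kg. The investigators' earlier cohorts had a mean catheterization of 6 days, about 12 doses at one every 12 hours, so more than one cycle is possible.

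**Who this could be.** At an assumed height of 1.65 m, 50-60 kg is a BMI of 18.4-22.0. The Appendix I 95th percentiles at age 14 are 26.05 (male) and 27.26 (female), so the range includes non-obese adolescents.

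**Timing against D2.** The Trial Flow Chart (note i) puts D1 before enoxaparin and D2 at 24±6 hours after D1, or with the anti-Xa draw. Note c puts the first anti-Xa level 4-6 hours after dose 3. With doses at 0, 12 and 24 hours, that level falls at 28-30 hours, and dose 4, at about 36 hours, is the first that can be titrated. D2 is thus drawn before or with the first level, and so before Step 3's cap can act. This reads the anti-Xa draw in note i as the first one.

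**The case against.** **The worksheet may simply complete Table 2.** Its factors match, and the Rationale for Dose Selection does not confine the maximum to the first dose. On this view Table 2 is silent rather than opposed. That is a fair reading, but it does not remove the problem. If 30 mg applies throughout, Table 2 orders an increase that cannot be given and asks for another level after the third dose, with no instruction for a child at the maximum. Either reading needs a correction.

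**The strategy still largely works under the cap.** A reader might infer that children above 50-60 kg cannot receive the anti-Xa-directed strategy at all. The documents do not support that. Monitoring, maintenance in range, decreases and holds all operate as written. Only upward steps are lost, fully from 60 kg and partly between 50 and 60 kg at the first step.

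**Few children may need an increase.** A reader might also put the share stuck below target at 24-36%. That takes the adult peaks under Pharmacokinetics, interpolates to 30 mg (0.16 + (0.38−0.16)×10/20 = 0.27 IU/mL), and assumes a normal distribution with SD 0.10-0.20. The upper SD matches the pilot, which had 9 samples from 4 children on heparin and is not an SD of peak enoxaparin levels. With SD 0.20 the model also puts about 9% of children below zero. The same section gives adult steady-state peaks of 1.1-1.2 IU/mL at 1 mg/kg every 12 hours. Scaled in proportion to 0.5 mg/kg, these become 0.55-0.60, and the same SDs put about 0-4% below 0.2. Both routes extrapolate from adults. The documents are compatible with anything from almost none to about a third, so no share should be quoted.

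**No weight or age distribution is given.** It therefore cannot be said that the effect falls mostly in the stratum above 13 years. On the doubled dose for obesity, the cap binds at much lower weights.

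**Conclusion.** The inconsistency stands. The protocol body and the worksheet give different ceilings for titrated doses, and a site cannot follow both once a child reaches 30 mg with a low level. The size per child is exact: 30 mg against 33 or 36 mg from 60 kg at the standard dose, with divergence from 50 or 54.5 kg at the first step; on the doubled dose, divergence starts at about 25-27 kg and the cap is reached at 30 kg. The number of children affected cannot be derived.

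A reader might infer that the main Aim 2 result is compromised. It is not, on this point: the posterior probability for ETP below 700 nM·min, and the 0.60 rule for the phase 3 dose, use D2, which precedes titration. What can be affected is time to target anti-Xa, ETP at D3 and D4, and the secondary models linking ETP and anti-Xa to each other and to clinical outcomes. That sites will in fact differ is a possibility the wording leaves open, not something the documents show.

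This is a moderate wording reconciliation. It should be made because it concerns the dose of study drug, but it does not threaten the primary analysis.

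**What to change.** 1. State once, in Treatment Regimen with Enoxaparin, whether the 30 mg maximum applies to the initial dose only or to all doses, including titrated doses in children whose initial dose was doubled.
2. Make Table 1, Table 2 and Appendix II Steps 2-3 agree with that statement. Table 2 and Step 3 should give the same dose for the same child.
3. If the maximum applies throughout, say what Table 2's repeat-level instruction means for a child already at the maximum and below target, and how such a child counts in the time-to-target analysis.

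Which rule is right is a clinical decision for the sponsor's team. The cost is a wording amendment to the tables and worksheet, a sentence in the analysis section if item 3 applies, and a memo to the six sites. No additional patients or procedures are needed.

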APPENDIX III

Bleeding in the PICU

Instructions for Assessors: Complete this form daily while the patient was admitted to the PICU. USE A SEPARATE FORM FOR EACH UNIQUE SITE OF BLEEDING.

* Required

1. Patient Study ID *

2. Study Collaborator *

3. Day of Admission in the PICU *

Day of admission to the PICU = Day 1. Please do NOT include days admitted to other units in the hospital.

4. Bleeding Site *

Choose the site of the bleeding event on this day. If the patient did not have a bleeding event on this day, select "No Bleeding Event."

Mark only one oval.

- ☐ No Bleeding Event *Stop filling out this form.*
- ☐ Vascular Catheter or Insertion Site *Skip to question 5.*
- ☐ Other Skin Bleeding (NOT CVC-Related) *Skip to question 7.*
- ☐ Gastrointestinal *Skip to question 8.*
- ☐ Respiratory (Including the Thoracic Cavity) *Skip to question 9.*
- ☐ Surgical Site *Skip to question 10.*
- ☐ Genitourinary *Skip to question 11.*
- ☐ Intra/Retroperitoneal *Skip to question 12.*
- ☐ Central Nervous System *Skip to question 13.*
- ☐ Eye, Ear, Nose, or Mouth *Skip to question 14.*
- ☐ Pericardium *Skip to question 17.*
- ☐ Joint *Skip to question 15.*
- ☐ Other (Describe) *Skip to question 16.*

Bleeding Site - Vascular or Catheter Insertion Site

5. Vascular or Catheter Insertion Site *

Mark only one oval.

- ☐ Peripheral Vein - Arm
- ☐ Peripheral Vein - Leg
- ☐ Femoral Vein
- ☐ Internal Jugular Vein
- ☐ Subclavian Vein
- ☐ Other:

6. Specify Side *

Mark only one oval.

- ☐ Left
- ☐ Right

Skip to question 17.

Bleeding Site - Other Skin Bleeding (NOT CVC-Related)

7. Other Skin Bleeding Site(s) - NOT CVC-Related *

Please select all that apply.

Check all that apply.

- ☐ Bruising
- ☐ Petechiae
- ☐ Non-Surgical Wound
- ☐ Other:

Skip to question 17.

Bleeding Site - Gastrointestinal

8. Gastrointestinal Bleeding Site *

Please select all that apply.

Check all that apply.

- ☐ Hematemesis
- ☐ Melena
- ☐ Hematochezia
- ☐ Other:

Skip to question 17.

Bleeding Site - Respiratory (Including the Thoracic Cavity)

9. Respiratory/Thoracic Cavity Bleeding Site *

Please select all that apply.

Check all that apply.

- ☐ ETT/Tracheostomy Aspirate
- ☐ Hemoptysis
- ☐ Hemothorax
- ☐ Other: _____

Skip to question 17.

Bleeding Site - Surgical Site

10. Surgical Bleeding Site *

Please select all that apply.

Check all that apply.

- ☐ Incision
- ☐ Drain/Tube
- ☐ Other: _____

Skip to question 17.

Bleeding Site - Genitourinary

11. Genitourinary Bleeding Site *

Please select all that apply.

Check all that apply.

- ☐ Gross Hematuria
- ☐ Bleeding Around a Urinary Catheter
- ☐ Menstrual Bleed (that required medical consultation or intervention)
- ☐ Other: _____

Skip to question 17.

Bleeding Site - Intra/Retroperitoneal

12. Intra/Retroperitoneal Bleed *

Please describe the location of the bleed.

...

Skip to question 17.

Bleeding Site - Central Nervous System**13. Central Nervous System Bleed ***

Please select all that apply.

Check all that apply.

- ☐ Epidural Bleed
- ☐ Subdural Bleed
- ☐ Subarachnoid Bleed
- ☐ Intraparenchymal Bleed
- ☐ Intraventricular Bleed
- ☐ Intraspinal Bleed (any site within the spinal column)
- ☐ Other: ...

Skip to question 17.

Bleeding Site - Eye, Ear, Nose, or Mouth**14. Eye, Ear, Nose, or Mouth Bleed ***

Please select all that apply.

Check all that apply.

- ☐ Subconjunctival Bleed
- ☐ Retinal Bleed
- ☐ Hemotympanum
- ☐ Epistaxis
- ☐ Oropharyngeal Bleed
- ☐ Other: ...

Skip to question 17.

Bleeding Site - Joint

15. Bleeding in the Joint *

Please specify which joint(s) is/are involved.

Check all that apply.

- ☐ Shoulder
- ☐ Elbow
- ☐ Wrist
- ☐ Finger
- ☐ Hip
- ☐ Knee
- ☐ Ankle
- ☐ Toe
- ☐ Other: _____

Skip to question 17.

Bleeding Site - Other (Describe)**16. Other Bleeding Site ***

Please describe the location of the bleed (if possible).

Skip to question 17.

Bleeding Severity

Please select AT LEAST one item from ONLY ONE of the bleeding severity categories below. Please select the most severe category as it applies to the bleeding event documented on this current day of admission. Remember to use a different form for another bleeding event on this same day but at a different site.

17. Major Bleeding

Please check all that apply.

Check all that apply.

- ☐ Fatal Bleeding
- ☐ Clinically Overt Bleeding with Decrease in Hgb of ≥ 2 g/dL in a 24-hr Period
- ☐ Bleed that is Intra/Retroperitoneal, Pulmonary, or Involves the CNS
- ☐ Bleeding Requiring Surgical Intervention in the Operating Room

18. Clinically Relevant Non-Major Bleeding

Please check all that apply.

Check all that apply.

- ☐ Overt Bleeding Requiring Blood Product Administration
- ☐ Bleeding that Requires Medical or Surgical Intervention NOT in the Operating Room (and Does NOT Include Menstrual Bleeding)

19. Minor Bleeding

Please check all that apply.

Check all that apply.

- ☐ Overt or Macroscopic Evidence of Bleeding that Does NOT Fulfill Above Criteria (for Major Bleeding or Clinically Relevant Non-Major Bleeding)
- ☐ Menstrual Bleeding Resulting in Medical Consult and/or Intervention

*Skip to question 20.***Timing****20. Type of Bleed ****Mark only one oval.*

- ☐ New Bleed
- ☐ Ongoing Bleed
- ☐ Recurrent Bleed at the Same Site

21. Bleeding Start Date

Please type which day of admission the bleed started.

22. Bleeding End Date

Please type which day of admission the bleed ended.

23. Started Prior to Today's Study Day? **Mark only one oval.*

- ☐ Yes
- ☐ No
